#### **8.6 Trial specific preventive measures**

The performance of a hearing aid is not impacted by medication. The subjects will continue to take whatever type of medication that they normally take. There will be no impact on the study objectives.

#### **8.7 Concomitant Interventions (treatments)**

Test subjects will continue to receive any concomitant care and medication that they normally receive during the use of the IMD. All test subjects will already be hearing aid users and will have, therefore, used the RMD while receiving other types of care or medications. There will be no impact on the study objectives.

#### **8.8 Medical Device Accountability**

The subjects will already be in possession of the RMD. The devices have serial numbers by which the individual device can be identified and the production history traced. The IMD will also have serial numbers to identify them. They will be shipped from the production site in Poland. The serial numbers will provide the traceability of their production and from which batch they came. Only IMD that are from a tested batch will be used in the study.

Page 29 of 50

CONFIDENTIAL

---

BF001-1611, Clinical Protocol, Version 3.0, Final, Version date 02.01.2017, Page 29 of 50

## **8.9 Return or Destruction of Study Drug / Medical Device**

At the end of the study all of the subjects will return the IMD to the site in Bern. It will be noted in the documentation that the devices were returned and whether the subject would like to return to the clinic to be fitted with the IMD once available for release.

**9. STUDY ASSESSMENTS****9.1 Study flow chart(s) / table of study procedures and assessments**

Study Periods	Intervention Period							Follow-up
	Screening/1	2	3	4	5	6	7	
Visit	14+/-3d	24+/-3d	38+/-3d	45+/-3d	59+/-3d	70+/-7d	Day	0
Patient Information and Consent	x							
Demographics	x							
Medical History	x							
In-/Exclusion Criteria	x							
Randomization	x *	x **					x **	
Otoscopy	x	x	x	x	x	x	x	x
Audiometry	x							
Real Ear Measurement	x		x			x		
Administer Medical Device	x		x			x		
Primary Variables (speech)		x					x	
Secondary Variables (interview)		x		x			x	
Other Variables (evaluation of questionnaire)		x		x			x	
Other Variables (usability)				x			x	
Adverse Events	x	x	x	x	x	x	x	x

\* Randomization of field trial period

\*\*Randomization of lab trial test conditions

## 9.2 Assessments of outcomes

### 9.2.1 Assessment of primary outcome

The primary outcome is the performance of the IMD compared with the RMD. It will be measured various times throughout the trial. The defining measurement will be on the 59th (+/-3d) of treatment when the subjects return to the clinic and will be measured with a questionnaire and lab tests. The results from this lab test will directly compare the IMD with the RMD as well as the unaided condition with no device. They will be compared to ensure that performance of the IMD is not poorer than the RMD.

### 9.2.2 Assessment of secondary outcomes

Subjective benefit regarding performance will be measured throughout the trial. Questionnaires will be collected and interviews conducted at 14, 38th, and 59th (+/- 3d).

### 9.2.3 Assessment of other outcomes of interest

Speech intelligibility will be assessed with the new feature on the 14 (+/- 3d). It will be assessed with speech in noise tests in a simulated environment in the clinic. The test conditions used will be made with the IMD with the feature on and off. The percentage of correct answers will be compared across conditions to ensure that speech intelligibility is not poorer with the new feature than without.

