Measurements and procedures:	
Amplification is verified and compared with targets using Real Ear Measured
 
Speech intelligibility tested in quiet or with background noise. Tests used include: Oldenburg Sentence Test (OLSA), Wallenberg and Kollmeier Rhyme Test (WaKo), Oldenburg Logatom Corpus (OLLO). Speech tests are normally set up with speech in the front and noise in the back or at varying degrees around the test client. Some tests such as the OLSA have a varying signal depending on the SNR goal, and others are set to specific speech and noise signal level.
 
Noise acceptance is tested with the Acceptable Noise Level (ANL) Test which uses the most comfortable listening level of the client and then allows the client to adjust the noise until it is too loud.
 
Interviews are conducted with the subjects in order to gather more information about their experience with the hearing aids. The interview is guided with questions but allows for open comments and topics driven by the subjects' comments
 
Preference testing is subjective testing that allows the test person to rate specific settings or devices when listening to the same sound environment.
 
Subjective perception of devices with questionnaires asks the test clients various questions concerning the expectations and benefits of the hearing devices. They can be answered for two different devices or settings and then compared again one another. The questionnaires are the Device Oriented Questionnaire (DOSO), the Abbreviated Profile of Hearing Aid Benefit (APHAB), Speech, Spatial, and Quality Questionnaire (SSQ), and the NASA Task Load Index. Questionnaires designed to address specific topics concerning the new device will be used.
 
Usability and handling is measured with the Practical Hearing Aid Skill Test which asks test clients to perform different handling activities with the devices. Other in-house questionnaires are also used that directly target new hardware or features of the hearing devices.

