### 9.3.2 Second Visit

Visit 2, Testing, Day 14 +/-3: The subjects will hand in the completed questionnaire given to them at the previous appointment. The clinician will conduct an interview based on the comments in the diary and prepared questions about user experience. They will be asked which pair of hearing aids they preferred. A lab test will be made to test speech intelligibility with the OLSA and WAKO tests (all features besides [REDACTED] will be set to off for the Lab testing). They will return the IMD and be instructed to use the RMD until the next appointment. Any AEs will be reported in the CRFs. They will be scheduled for the next visit.

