2.1 Reference study search and summary

The following references give an overview about similar reported trials in order to estimate the benefit of amplification (unaided-aided) for an adaptive speech in noise test. Benefit of amplification with commercially available devices on the 50% speech reception threshold are described regarding test set-up differences:

- 1. 08VM from **Valente & Mispagel (2008)** mean difference of 1.6 dB SNR (sd = na) on 26 subjects with a mild to moderate-severe hearing loss (mean age = 65.6). Open fitted hearing aids from Vivatone. Speech (HINT) at 65 dB and 8 noise sources.
- 2. 08KD from Klemp & Dhar (2008) mean difference of 2.3 dB SNR (sd = na) on 16 subjects with a

mild to moderate hearing loss (age 50-85). Open fitted hearing aids from Phonak and Widex. Speech at 65 dB A (HINT) and 3 noise sources.

[figure not shown]
- 3. 10AP from **Alworth & Plyler (2010)** mean difference of 1.5 dB SNR (sd = 2.3) on 25 subjects with a mild to moderate hearing loss (mean age = 67). Open fitted hearing aids from Bernafon with NL1. Speech at fixed level (HINT) and 1 noise source from the front.
- 4. 13MT from **Magnusson et al. (2013)** mean difference 1.6 dB SNR (sd = 2.0) on 20 subjects with a mild hearing loss (age 51-64). Open fit with hearing aids from Phonak (own fitting rationale). Speech at 65 dB SPL (Swedish Hagermann) and 4 noise sources.
- 5. 13HW from **Helbling et al. (2013)** mean difference 2.3 dB SNR (sd = 1.4) on 20 subjects with a moderate hearing loss (age 42-77). Open fit with hearing aids from Sonic Innovation (own fitting rationale). Noise at 65 dB SPL (OLSA) and 1 noise source from the front.
- 6. 15WA from **Woods et al. (2015)** mean difference 2 dB SNR (sd = 2.3) on 24 subjects with a mild to moderate-severe hearing loss (age 61-81). Open fit with hearing aids from Phonak and GN. Speech at 70 dB SPL (HINT) and ? noise sources.
- 7. 16REF from unpublished **internal test (2016)** mean difference 2 dB SNR (sd = 2.0) on 35 subjects with a mild to moderate-severe hearing loss (age 37-87). Fitting with domes and custom molds from Bernafon Reference hearing aid (Juna 9). Speech at 65 dB SPL (OLSA) and 4 noise sources.

study	spatial.noise	speech.mat	plateform	main.effect	standev	sample.size	ci.low	ci.high
08VM	separated	other	different	1.6	NA	26	NA	NA
08KD	separated	other	different	2.3	NA	16	NA	NA
10AP	colocated	other	same	1.5	2.3	25	0.55	2.4
13MT	separated	other	different	1.6	2.0	20	0.67	2.5

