13HW	colocated	olsa	same	2.3	1.4	20	1.65	3.0
15WA	colocated	other	different	2.0	2.3	24	1.03	3.0
16REF	separated	olsa	same	2.0	2.0	35	1.31	2.7

The last reference (16REF) comes from internal test results with the reference marketed device in the same test setup that is planned to be used for the current investigation. The summary of all these studies can be shown in the following graph:

Studies 08KD and 08VM are shown even no confidence interval could be computed based on the reported results. The summary estimation will therefore exclude these two studies.

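### Percentage correct is the stated measure for the Day 14 feature on/off speech comparison, and it does not suit OLSA if OLSA is run adaptively as the documents describe it

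*Protocol*

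**What the plan says.** Speech intelligibility with the new feature on and off is a secondary endpoint (Protocol synopsis and 5.2) and serves the secondary objective in 4.3. Section 9.2.3 is where its Day 14 scoring is described. It says of the assessment: "It will be assessed with speech in noise tests in a simulated environment in the clinic". It names no test, and then gives the measure: "The percentage of correct answers will be compared across conditions to ensure that speech intelligibility is not poorer with the new feature than without".

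The tests are named in 9.3.2, for Visit 2 (Day 14): "A lab test will be made to test speech intelligibility with the OLSA and WAKO tests".

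On how the tests are presented, the synopsis (Measurements and procedures) draws a distinction: "Some tests such as the OLSA have a varying signal depending on the SNR goal", whereas "others are set to specific speech and noise signal level". It does not say to which kind WaKo belongs.

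SAP 2.1 gathers its reference studies, two of which used OLSA, to "estimate the benefit of amplification (unaided-aided) for an adaptive speech in noise test". It describes the quantity as "Benefit of amplification with commercially available devices on the 50% speech reception threshold". It adds that the internal 2016 OLSA test was done "in the same test setup that is planned to be used for the current investigation". Protocol 5.1, 9.3.6 and 11.4.2 accordingly analyse the Visit 6 OLSA as an SRT.

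**The concern.** An adaptive speech test makes the signal harder after good responses and easier after poor ones until the score settles at a chosen level, here 50%. Percentage correct is what the procedure holds constant, and the signal-to-noise ratio at which it settles is the result. If the Day 14 OLSA is run this way, comparing percentages with the feature on and off compares two numbers that both sit near 50%, whatever the feature does.

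The lack of sensitivity also favours the sponsor. The aim is to show that the feature does no harm to speech understanding, and a measure that barely moves will tend to look reassuring. The feature is the one new processing element in the device, and Protocol 3.1 says that its effectiveness needs to be evaluated.

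**Working it through.** **Figures in the plan.** The documents give no sample size, margin or power for the on/off comparison, so there is no figure to reproduce for it. The stated 24 subjects belong to the primary SRT test. With the SAP section 4 inputs, (2 × (1.960 + 1.282) / 1.34)² = 23.4, rounded up to 24. Nothing below changes that.

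**The sections side by side**

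1. 9.2.3 sets percentage correct for the Day 14 on/off comparison, without naming a test.
2. 9.3.2 lists OLSA and WaKo for that visit. As written, the measure therefore covers both.
3. The synopsis and SAP 2.1 describe OLSA as adaptive and read at the 50% threshold.
4. At Visit 6 the protocol scores OLSA as an SRT. It gives no reason for scoring it differently at Visit 2.

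**Size of the effect.** This was checked by simulation. These inputs are assumptions and are not in the documents:

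- a logistic curve for the proportion of words correct, p = 1 / (1 + exp(−4 × slope × (SNR − SRT))), with slope 0.10, 0.15 or 0.20 per dB;
- SRT of −5 dB SNR with the feature off and −3.7 dB SNR with it on, a true loss of 1.3 dB;
- 20 sentences of five words starting at 0 dB SNR, the first five dropped, with shrinking steps proportional to the departure from 50%; 20,000 tracks per condition.

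The 1.3 dB is used only as a convenient size of loss.

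Fixed-level scores follow directly from the formula when both conditions are tested at −5 dB SNR. The off score is 50%. The on score is 1 / (1 + exp(4 × slope × 1.3)), which for slope 0.10 is 1 / (1 + exp(0.52)) = 37.3%.

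| Slope (points per dB) | Adaptive % correct, off vs on | Adaptive SRT, off vs on (dB SNR) | SRT difference (dB) | Fixed-level % correct, off vs on |
|---|---|---|---|---|
| 10 | 50.4 vs 50.2 | −4.96 vs −3.67 | 1.29 | 50.0 vs 37.3 |
| 15 | 51.0 vs 50.5 | −4.93 vs −3.67 | 1.26 | 50.0 vs 31.4 |
| 20 | 51.9 vs 50.9 | −4.90 vs −3.65 | 1.25 | 50.0 vs 26.1 |

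The adaptive percentage moves by 0.2, 0.5 and 1.0 points. The fixed-level percentage falls by 12.7, 18.6 and 23.9 points. Over true losses of 1 to 2 dB, the largest adaptive change was 51.9 − 50.6 = 1.3 points; the fixed-level change ran from 50.0 − 40.1 = 9.9 to 50.0 − 16.8 = 33.2 points. The exact sizes depend on the assumed slope and step rule. The direction follows from how an adaptive track works.

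**The case against.** The strongest objection is that no section says how OLSA is run on Day 14. The synopsis is a general catalogue of tests. SAP 2.1 concerns unaided versus aided benefit, and its remark about the same set-up supports the margin for the investigational versus the reference device. Section 9.2.3 does specify Day 14 scoring, and its choice of percentage correct could itself indicate fixed-level presentation. That would be a reasonable design: the feature responds to the signal-to-noise ratio (Protocol 3.1), and an adaptive track could settle at different ratios with the feature on and off. This objection stands, and it makes the point conditional. It does not remove it, because a fixed-level OLSA would depart from the documents' own description of the test and would need to be stated.

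Three stronger readings are tempting, and the documents do not support them.

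- *The whole on/off comparison cannot show a difference.* WaKo is also tested at Visit 2 and has its own line in the CRF (12.1.1). If it is run at fixed levels, as the synopsis suggests without naming it, its percentage correct can show a feature effect.
- *A finding of no harm is guaranteed by construction.* Section 11 gives no test, margin or decision rule for the on/off comparison, and nothing says that the conclusion rests on the OLSA percentage alone.
- *The 1.3 dB margin is the standard that would be missed.* That margin was set for the investigational versus the reference device (Protocol 11.1, SAP 3.1). None is given for feature on versus off.

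**Conclusion.** The point holds in a limited, conditional form. If OLSA is run adaptively on Day 14, as the general descriptions indicate, the measure in 9.2.3 is practically insensitive for that test: a 1.3 dB loss shifts it by 1 point or less on the assumed slopes, while the SRT shows nearly all of the loss. This is more than a missing detail, because a stated measure does not fit the test as the documents describe it.

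The consequence is modest. The comparison is secondary, in a study that the protocol calls exploratory. The primary SRT analysis and its sample size are untouched. The conclusion rests on two inferences, that the Day 14 OLSA is adaptive and that WaKo is run at fixed levels, and the protocol should confirm both.

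**What to change.** In Protocol 9.2.3:

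- State for each Day 14 test whether it is adaptive or run at fixed speech and noise levels.
- If OLSA is adaptive, compare it by the paired SRT difference in dB SNR, feature on minus off, with a 95% confidence interval. A lower SRT is better, so a positive difference means worse with the feature. This sign is opposite to the control-minus-test convention in 11.1 and should be written out.
- Keep percentage correct for any test run at fixed levels: WaKo if that is its mode, and OLSA if it is run that way.

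The cost is two or three sentences. An adaptive OLSA already yields the SRT and the CRF already has a line for OLSA results; it is enough to make sure that this line records the SRT. No extra visits, tests or subjects are needed.

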### 9.2.4 Assessment of safety outcomes

The test participants will be asked to keep a diary during the field trial and to write down anything unexpected that occurs. Unexpected events or effects include feedback or whistling from the device, unexpected sounds or artefacts from the device, discomfort, muting or shutting off of the device in mid-use, unexplained warning signals or beeping from the device, loud sounds, and occlusion. The information provided from the field trial will alert the testers to the potential for safety risks that should be addressed before the product is released to the market. It is not expected that any of these things will occur and have not during testing on previous products.

#### 9.2.4.1 Adverse events

For the recording of adverse events the subjects will be instructed to write in their diary a description of the event including how long it lasted, how many times it occurred, and if it caused discomfort or pain or a disruption of hearing ability.

#### 9.2.4.2 Laboratory parameters

Not applicable

#### 9.2.4.3 Vital signs

Not applicable

### 9.2.5 Assessments in participants who prematurely stop the study

After the study concludes the subjects will return the IMD. The follow-up procedure will be the same as for all active test subjects. They will be instructed to return to the clinic for any required maintenance or fine-tuning of the devices. Those that withdraw prematurely will already be wearing their RMD Bernafon devices; therefore, their follow-up treatment will be the same.

## 9.3 Procedures at each visit

### 9.3.1 Screening/First Visit

Screening visit, Day 0: Otoscopy is performed. Air and bone audiometry is performed to determine hearing loss. A history is taken that includes hearing history as well as general health history. The Patient Informed consent form will be explained to the subject and given to read, sign, and date. No trial activities will be performed before the Patient Informed consent form is signed and dated by the subject and investigator. Patients are given time during the appointment to decide, whether or not to participate in the study. Subjects will receive a copy of the signed patient informed consent form and the patient information. Inclusion/exclusion criteria will be determined. The trial will be explained including how many visits are expected as well as the type of testing that they will complete. The subjects will be fit with a pair of IMD with [REDACTED] programmed and a second pair of IMD without [REDACTED]. Output will be measured with Real Ear Equipment. All other features will be set as prescribed by the software. They will receive an Instructions for Use (IFU). They will be given a questionnaire ([REDACTED]) and a diary to keep during the first period of the field trial. They will be scheduled for the First Visit. Any AEs will be reported in the CRFs.

### 9.3.2 Second Visit

Visit 2, Testing, Day 14 +/-3: The subjects will hand in the completed questionnaire given to them at the previous appointment. The clinician will conduct an interview based on the comments in the diary and prepared questions about user experience. They will be asked which pair of hearing aids they preferred. A lab test will be made to test speech intelligibility with the OLSA and WAKO tests (all features besides [REDACTED] will be set to off for the Lab testing). They will return the IMD and be instructed to use the RMD until the next appointment. Any AEs will be reported in the CRFs. They will be scheduled for the next visit.

### 9.3.3 Third Visit

Visit 3, Fitting, Day 24 +/-3: The subjects will be fit with the IMD. Output will be measured with Real Ear Equipment. All settings will be set to the defaults. They will be instructed to wear the IMD for the entire trial period. They will be given two questionnaires (specific to the device and the DOSO) and a diary to keep during the field trial. Any AEs will be reported in the CRFs. They will be scheduled for the next visit.

### 9.3.4 Fourth Visit

Visit 4, Testing, Day 38 +/- 3: The subjects will hand in the completed questionnaires given to them at the previous appointment. The clinician will conduct an interview based on the comments in the diary and prepared questions about user experience. The clinician will complete a PHAST test with the subject for usability of the IMD. They will return the devices and be instructed to use the RMD until the next appointment. Any AEs will be reported in the CRFs. They will be scheduled for the next visit.

### 9.3.5 Fifth Visit

Visit 5, Fitting, Day 45 +/- 3: The subjects will be fit with the IMD. Output will be measured with Real Ear Equipment. The subjects will be given three questionnaires (two device specific questionnaires and APHAB) and a diary to keep during the field trial. They will be instructed to wear the IMD for the entire trial period. Any AEs will be reported in the CRFs. They will be scheduled for the next visit.

### 9.3.6 Sixth Visit

Visit 6, Testing/Final, Day 59 +/- 3: The subjects will hand in the questionnaires given to them at the previous appointment. The clinician will conduct an interview based on the comments in the diary and prepared questions about user experience. A lab test will be made to test speech intelligibility with the OLSA. They will test in three conditions: unaided, aided with the RMD, and aided with the IMD. Any AEs will be reported in the CRFs. They will be told that the trial is complete.

### 9.3.7 Follow-Up

Visit 7, Follow-up, Day 70+/- 7: If subjects choose to have the RMD fine-tuned, they will make appointments as needed for follow-up adjustments and maintenance.

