## STUDY SCHEDULE

A tabular listing of schedule of events and assessments and procedures of the study

Study Periods	Intervention Period						Follow-up
	Visit	Screening/1	2	3	4	5	6
Day	0	14+/-3d	24+/-3d	38+/-3d	45+/-3d	59+/-3d	70+/-7d
Patient Information and Consent	x						
Demographics	x						
Medical History	x						
In-/Exclusion Criteria	x						
Randomization	x *	x **					x **
Otoscopy	x	x	x	x	x	x	x
Audiometry	x						
Real Ear Measurement	x		x			x	
Administer Medical Device	x		x			x	
Primary Variables (speech)		x					x
Secondary Variables (interview)		x		x		x	
Other Variables (evaluation of questionnaire)		x		x		x	
Other Variables (usability)				x		x	
Adverse Events	x	x	x	x	x	x	x

\* Randomization of field trial period

\*\*Randomization of lab trial test conditions

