#### **8.5 Data Collection and Follow-up for withdrawn participants**

Withdrawn subjects' data will not be used in any final data analysis or report. Any data that is collected prior to withdrawal will be kept in the data management database. The data will remain encoded because results are only recorded using the identification code of the subject. Withdrawn subjects will have the same follow-up as those subjects that complete the trial. They will already be Bernafon hearing aid users and, therefore, welcome to return to the clinic for follow-up fine tuning and maintenance as needed.

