## 10. SAFETY

### 10.1 Medical Device Category C studies

All adverse events (AE) including all serious adverse events (SAE) are collected, fully investigated and documented in the source document and appropriate case report form (CRF) during the entire study period, i.e. from patient's informed consent until the last protocol-specific procedure, including a safety follow-up period. Documentation includes dates of event, treatment, resolution, assessment of seriousness and causal relationship to device and/or study procedure.

The information on AEs is systematically collected by the clinician at each study visit. They will follow the procedures outlined in SOP-Medical Device Incident Reporting. The subjects are asked to keep a diary and write down any unexpected events. During the regular clinic visits the subjects are then asked questions about the event to gather details and to determine the severity of the event. If a subject reports pain that results in the inability to use the device he will be withdrawn from the study in order to avoid any pain from using the device and to remove partial data from the study. For reports of pain caused by insertion or the dome itself, the problem can be addressed in the clinic. For example, a different style or size of dome can be placed on the hearing aid, and re-training of insertion can be performed with the subject to avoid wrong or forceful insertion of the device. For reported pain they will be advised to not wear the device for 24 hours before resuming use.

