#### **11.5 Handling of missing data and drop-outs**

For missing data, the PI will contact the involved subject to evaluate the possibility of getting missing data from a questionnaire by post. If a test subject cannot come to the evaluation visit, after exhausting all the possibilities to reschedule a new one, the devices will be sent back per post. If a subject does not want to adhere to the protocol, he can easily switch back to his own device (RMD) and return the IMD.

Data will be immediately removed if the PI has some doubts about the data accuracy (especially about the understanding of the APHAB questionnaire).

Dropouts will not be replaced; therefore, extra subjects over the calculated sample amount will be included from the beginning to ensure enough completed cases with all data.

Analysis will be done on the complete case only.

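### The schedule gives every participant an adverse-event check at Day 70, but the visit text makes that visit optional, so collection of events after the last IMD period is not assured

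*Protocol*

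**What the plan says.** **Schedule.** The Study Schedule, repeated in Protocol 9.1, ends with a follow-up column at Day 70 ± 7. The two safety rows are filled throughout: "Adverse Events x x x x x x x" and "Otoscopy x x x x x x x". No footnote makes the follow-up visit conditional.

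**AE rules.** Protocol 10.1 sets the collection period as "from patient's informed consent until the last protocol-specific procedure, including a safety follow-up period" and has the clinician gather AE information at every study visit. It gives no length for the safety follow-up period.

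**Visit text.** Protocol 9.3.6 (Visit 6, Day 59 ± 3) has a diary-based interview, the speech test and AE recording. It then says of participants: "They will be told that the trial is complete". Protocol 9.3.7 (Visit 7, Day 70 ± 7) consists of one sentence: "If subjects choose to have the RMD fine-tuned, they will make appointments as needed for follow-up adjustments and maintenance".

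**Withdrawals and missed visits.** Protocol 8.5 states: "Withdrawn subjects will have the same follow-up as those subjects that complete the trial". Protocol 9.2.5 describes that follow-up as returning for maintenance or fine-tuning as required. For a participant who cannot attend an evaluation visit, Protocol 11.5 says that "after exhausting all the possibilities to reschedule a new one, the devices will be sent back per post". It mentions no AE contact.

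**The concern.** Staff who work from the schedule and 10.1 would see every participant at Day 70 and ask about AEs. Staff who work from 9.3 would end the trial at Day 59 and see only those who ask for an adjustment of their own device. Both cannot be followed.

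The safety information matters here. Finding unknown or unwanted behaviour of the IMD is a second primary objective (4.2). There are no earlier clinical data on the IMD (3.4) and no data safety monitoring committee (1.6). The safety analysis rests on the investigator's interview and judgement (11.4.5). The foreseeable events in 10.1 include skin reaction and domes or filters coming off in the ear, and these could be noticed or develop after wear has stopped. If 9.3.7 is followed, the participants observed after the last IMD period are selected by their wish for RMD fine-tuning. That is not a safety criterion, and the post-wear AE record would be incomplete in an unknown way.

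**Working it through.** No stated figure of the plan is at issue. The check compares the texts and then measures the window.

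**1. Is the Day 70 visit conditional anywhere in the schedule?** No. In the available text the columns of the copy in 9.1 are shifted. The AE and otoscopy rows are full in both copies, so this reading does not depend on alignment.

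**2. How does 9.3.7 differ from the other visit texts?**
- 9.3.1 to 9.3.6 each contain a sentence sending AEs to the case report form. 9.3.7 does not.
- 9.3.1 to 9.3.5 each end by booking the next appointment. 9.3.6 does not, and it announces the end of the trial instead.
- 6.1 describes contact after the last appointment as a reminder that maintenance is available.

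**3. Does 10.1 settle it?** Not alone. If Visit 7 is only optional maintenance, the last protocol-specific procedure could be taken to be the Visit 6 test ("A lab test will be made to test speech intelligibility with the OLSA"). The safety follow-up period would then have no visit attached and no stated length.

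**4. How long is the window?** Inputs are the visit days and tolerances in the Study Schedule. Nominal gap = later day − earlier day. The range subtracts and adds both tolerances.

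| IMD period ends | Next visit | Nominal gap | Range | Status of next visit |
|---|---|---|---|---|
| Visit 2, Day 14 ± 3 | Visit 3, Day 24 ± 3 | 24 − 14 = 10 days | 21 − 17 = 4 to 27 − 11 = 16 | Required, AEs recorded |
| Visit 4, Day 38 ± 3 | Visit 5, Day 45 ± 3 | 45 − 38 = 7 days | 42 − 41 = 1 to 48 − 35 = 13 | Required, AEs recorded |
| Visit 6, Day 59 ± 3 | Visit 7, Day 70 ± 7 | 70 − 59 = 11 days | 63 − 62 = 1 to 77 − 56 = 21 | Conditional in 9.3.7 |

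Only the third period is followed by a visit that the visit text does not assure.

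**5. What is captured despite this?** Visit 6 includes the diary interview and AE recording, so events present by Day 59 are covered. The gap concerns events that begin, persist, worsen or resolve later.

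**The case against.** The strongest reply is that the requirement already exists. The schedule and 10.1 call for AE collection at follow-up, 9.3.7 numbers Day 70 as a visit, and its conditional clause could govern only extra fine-tuning appointments. That reading is possible. It fits poorly with 9.3.6, which closes the trial on Day 59 and books nothing further, and 9.3.7 gives Visit 7 no other content. The reply shows that the defect is a contradiction and not the absence of any requirement.

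It is also fair that Visits 3 and 5 are refitting visits which no section calls post-wear safety checks, and that the second may fall one day after wear ends. They are a useful comparison, not a standard set by the plan. The protocol further calls the foreseeable events improbable (10.1) and reports no adverse events for the sponsor's products in 15 years (3.4). That lowers the expected number of missed events but does not reconcile the texts.

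Four stronger readings that a reader might infer are not supported:
- **That the third IMD period has no AE check.** Visit 6 checks it. Only what follows Day 59 is open.
- **That withdrawn participants have no safety follow-up at all.** 8.5 and 9.2.5 give them the same follow-up as completers, with the same uncertainty. 12.1.2 also requires a case report form and a withdrawal reason, although 7.4 lets participants withhold the reason. Nothing says that withdrawals are usually caused by device problems.
- **That 9.3.7 drops otoscopy because it does not name it.** 9.3.2 to 9.3.6 do not name it either, although the schedule marks it at each of those visits. The missing AE sentence is what sets 9.3.7 apart.
- **That return of the IMD is left open.** 8.9 requires it at the end of the study and has it documented.

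The table of contents also lists a section on follow-up of (serious) adverse events whose text is not in the available document. It may cover AEs already known and ongoing. The secure part of the point is therefore newly emerging events and the contradiction itself.

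**Conclusion.** The point holds as an internal contradiction that affects the completeness of safety data. The schedule and 10.1 require AE collection after the last IMD period; 9.3.6 and 9.3.7, as written, do not assure it. The window is nominally 11 days, from 1 to 21, for any of about 35 participants who do not ask for RMD fine-tuning. How many that would be cannot be derived from the documents, nor can an expected number of missed events.

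This assumes that IMD wear ends at Visit 6, which follows from the end-of-trial message there together with 8.9, and that visit tolerances can combine freely. Withdrawn participants share the same ambiguity, and 11.5 adds a route, posting devices back, with no stated AE contact. The primary comparison of speech reception thresholds is not affected. The correction should be made because safety is a stated objective and the change is small.

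**What to change.** Reconcile the Study Schedule (and its copy in 9.1) with 9.3.6, 9.3.7 and 10.1, so that the Day 70 AE assessment already scheduled applies to all participants whether or not they want RMD fine-tuning:

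- **9.3.7:** state that Visit 7 is for all participants, add the AE-recording sentence used in the other visit texts, and describe RMD fine-tuning as the optional part.
- **9.3.6:** book Visit 7, and replace the end-of-trial message with one saying that testing is finished and follow-up remains.
- **10.1:** state the length of the safety follow-up period and tie it to Visit 7.
- **8.5, 9.2.5 and 11.5:** say how and when AEs are collected from participants who withdraw or post their devices back.

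The mode of contact and the extent of examination are for the sponsor to decide, consistent with what the schedule marks at follow-up.

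The cost is a wording amendment, plus follow-up contact for about 35 participants that the schedule already contains. Sample size and the primary analysis do not change.
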